4.3.1.4. Subgroup analysis

Not applicable.

4.3.2. Secondary efficacy estimand

The secondary estimand of interest is the effect of the treatments on symptoms reported by the patients in all patients assuming non-occurrence of IEs. The motivation for this choice is the same as the primary estimand.

Compared to the primary estimand, only the *variable* attribute is different and is defined as the change in ESSPRI total score from baseline to W013 (secondary efficacy endpoints). The ESSPRI total score is derived as the mean of 3 items. The other attributes, main and sensitivity analyses are the same as for the primary estimand.

In the same line as for the primary estimand, the supplementary analyses will be performed on the responders ESSPRI at W013 defined as patients having improvement from baseline in ESSPRI total score of at least:

- 1 point
- 2 points
- 3 points

using the same model as for responders ESSDAI.

4.3.3. Additional estimands based on ESSDAI and ESSPRI

Treatment policy estimands

Treatment policy estimands are defined in order to assess the treatment effect on the clinical disease activity (ESSDAI total score) and also on the symptoms reported by the patients (ESSPRI total score) regardless of whether or not the IE occurs.

The attributes of the additional estimands are defined as follow:

- Treatment: S95011 or placebo.
- Population: RS.
- Variable 1: change in ESSDAI total score from baseline to W013.
- Variable 2: change in ESSPRI total score from baseline to W013.
- Summary measure: difference in means between treatments.
- Intercurrent events: The occurrence of IEs (see list in primary estimand) is irrelevant in defining the treatment effect of interest. All observed values will be used regardless of occurrence of an IE.

Missing data not due to IE will be handled according to the MAR assumption as in the primary analysis.

Main analysis is the same as for the primary estimand. Supplementary analysis will be performed as for the primary estimand but considering the responders in ESSDAI at W013 defined as patients having improvement from baseline in ESSDAI total score of at least:

- 3 points

as well as on the responders in ESSPRI at W013 defined as patients having improvement from baseline in ESSPRI total score of at least:

- 1 point

using the same model as for responders ESSDAI for the primary estimand (Section 4.3.1.3).

Other estimand

This estimand of interest is the effect of the treatments on the composite response to treatment taking into account a double dimension - clinical disease activity from ESSDAI and symptoms reported by the patients from ESSPRI - in all patients assuming non-occurrence of IEs. The motivation for this choice is the same as the primary estimand.

The attributes of this estimand are defined as follows:

- Treatment: S95011 or placebo.
- Population: all randomised patients (RS).
- Variable: Number of responders defined as patients with ≥ 3 points of improvement in ESSDAI and with ≥ 1 point of improvement in ESSPRI from baseline at W013.
- Summary measure: difference in proportion between treatments.
- Intercurrent events (IE):
 - IE1: Study drug discontinuation for major worsening of primary Sjögren's syndrome.
 - IE2: Increase or initiation of authorized medication for pSS.
 - IE3: Study drug discontinuation for AE related to study drug.
 - IE4: Study drug discontinuation for other reasons (non-medical reason, AE not related...).
 - IE5: Switch of treatment group (error of dispensation).
 - IE6: Decrease or stop of authorized medication for pSS.

Note: In case a patient is concerned by several IEs, the first event will be considered. If several IE occurred the same day, IE will be considered to be more conservative in the following order: IE1; IE2; IE3; IE4; IE5, IE6. S95011 will be compared to placebo on the responders in the RS using a logistic regression model including the fixed, categorical effect of treatment and randomization stratification factors (*rando_factor*) as well as the continuous fixed covariate of baseline value of each score.

LOGISTIC REGRESSION MODEL:

$$\text{responder} = \text{baseline_ESSDAI baseline_ESSPRI rando_factors treatment} \quad [3]$$

The assumptions underlying the model, as for instance, independence of errors, linearity in the logit for continuous variables, absence of multicollinearity, and lack of strongly influential outliers will be checked.

If the model is not running due to too few patients in the stratas, the model mentioned above will be modified. Thus, the two stratification factors in the model will be replaced by the following composite factor: baseline intake of oral corticosteroids or antimalarial or both (yes/no). If the model is still not running with the stratification factor in two classes, then the stratification factor will not be considered.

The handling of IEs and missing data will be the same as the primary analysis of the primary estimand for continuous ESSDAI and ESSPRI respectively. Then, imputed change will be turned into responder/non responder separately for each score (ESSDAI 3 points and ESSPRI 1 point). Finally, the response to the composite endpoint will be derived. Sensitivity and supplementary analyses are not planned for this estimand.

4.3.4. Additional estimand based on STAR

This estimand aims at evaluating the effect of the treatments on Sjogren's Tool for Assessing Response (STAR): a composite score, in all patients assuming non-occurrence of IEs. The motivation for this choice is the same as the primary estimand.

The attributes of these estimands are defined as follows:

- Treatment: S95011 or placebo.
- Population: RS.

- Variable 1: proportion of responders in STAR score at W013 defined as patients with a STAR score ≥ 5 .
- Summary measure: difference in proportion between treatments.
- Intercurrent events (IE):
 - IE1: Study drug discontinuation for major worsening of primary Sjögren's syndrome.
 - IE2: Increase or initiation of authorized medication for pSS.
 - IE3: Study drug discontinuation for AE related to study drug.
 - IE4: Study drug discontinuation for other reasons (non-medical reason, AE not related...).
 - IE5: Switch of treatment group (error of dispensation).
 - IE6: Decrease or stop of authorized medication for pSS.

Note: In case a patient is concerned by several IEs, the first event will be considered. If several IE occurred the same day, IE will be considered to be more conservative in the following order: IE1; IE2; IE3; IE4; IE5, IE6. S95011 will be compared to placebo on the responders in the RS using a logistic regression model including the fixed, categorical effect of treatment and randomization stratification factors (*rando_factor*).

LOGISTIC REGRESSION MODEL:

$$\text{responder} = \text{rando_factors treatment} \quad [4]$$

The assumptions underlying the model, as for instance, independence of errors, linearity in the logit for continuous variables, absence of multicollinearity, and lack of strongly influential outliers will be checked.

If the model is not running due to too few patients in the stratas, the model mentioned above will be modified. Thus, the two stratification factors in the model will be replaced by the following composite factor: baseline intake of oral corticosteroids or antimalarial or both (yes/no). If the model is still not running with the stratification factor in two classes, then the stratification factor will not be considered.

The handling of IEs and missing data will be in the same line as the primary analysis of the primary estimand, but imputation will be done directly on the response variable. Sensitivity and supplementary analyses are not planned for this estimand.

4.3.5. Additional estimand based on CRESS

This estimand aims at evaluating the effect of the treatments on the Composite of Relevant Endpoints in Sjögren's Syndrome (CRESS): a composite score, in all patients assuming non-occurrence of IEs. The motivation for this choice is the same as the primary estimand.

The attributes of these estimands are defined as follows:

- Treatment: S95011 or placebo.
- Population: RS.
- Variable 1: proportion of responders in CRESS at W013 defined as patients with a response on ≥ 3 of the 5 items.
- Summary measure: difference in proportion between treatments.
- Intercurrent events (IE):
 - IE1: Study drug discontinuation for major worsening of primary Sjögren's syndrome.
 - IE2: Increase or initiation of authorized medication for pSS.

- IE3: Study drug discontinuation for AE related to study drug.
- IE4: Study drug discontinuation for other reasons (non-medical reason, AE not related...).
- IE5: Switch of treatment group (error of dispensation).
- IE6: Decrease or stop of authorized medication for pSS.

Note: In case a patient is concerned by several IEs, the first event will be considered. If several IE occurred the same day, IE will be considered to be more conservative in the following order: IE1; IE2; IE3; IE4; IE5, IE6. S95011 will be compared to placebo on the responders in the RS using a logistic regression model including the fixed, categorical effect of treatment and randomization stratification factors (*rando_factor*).

LOGISTIC REGRESSION MODEL:

$$\text{responder} = \text{rando_factors treatment} \quad [4]$$

The assumptions underlying the model, as for instance, independence of errors, linearity in the logit for continuous variables, absence of multicollinearity, and lack of strongly influential outliers will be checked.

If the model is not running due to too few patients in the stratas, the model mentioned above will be modified. Thus, the two stratification factors in the model will be replaced by the following composite factor: baseline intake of oral corticosteroids or antimalarial or both (yes/no). If the model is still not running with the stratification factor in two classes, then the stratification factor will not be considered.

The handling of IEs and missing data will be in the same line as the primary analysis of the primary estimand, but imputation will be done directly on the response variable. Sensitivity and supplementary analyses are not planned for this estimand.

4.3.6. Additional estimands based on other efficacy endpoints

These estimands of interest are the effect of the treatments on global assessments of the disease activity reported by the physician (PhGA) and by the patient (PGA), and tear and salivary glands function (Schirmer test, OSS and salivary test), in all patients assuming non-occurrence of IEs. The motivation for this choice is the same as the primary estimand.

The attributes of these estimands are defined as follows:

- **Treatment:** S95011 or placebo.
- **Population:** RS.
- **Variable 1:** change in PhGA score from baseline to W013.
- **Variable 2:** change in PGA total score from baseline to W013.
- **Variable 3:** change in Schirmer test from baseline to W013 (on the most affected eye and mean of both eyes).
- **Variable 4:** change in OSS from baseline to W013 (on the most affected eye and mean of both eyes).
- **Variable 5:** change in unstimulated salivary flow score from baseline to W013.
- **Summary measure:** difference in means between treatments.
- **Intercurrent events (IE):**
 - IE1: Study drug discontinuation for major worsening of primary Sjögren's syndrome.
 - IE2: Increase or initiation of authorized medication for pSS.

- IE3: Study drug discontinuation for AE related to study drug.
- IE4: Study drug discontinuation for other reasons (non-medical reason, AE not related...).
- IE5: Switch of treatment group (error of dispensation).
- IE6: Decrease or stop of authorized medication for pSS.

Note: In case a patient is concerned by several IEs, the first event will be considered. If several IE occurred the same day, IE will be considered to be more conservative in the following order: IE1; IE2; IE3; IE4; IE5, IE6. Main analyses are the same as for the primary estimand. Sensitivity and supplementary analyses are not planned for these estimands.

4.3.7. Descriptive analyses

For all efficacy endpoints, descriptive statistics will be provided at each visit, by treatment group and also for some efficacy endpoints (ESSDAI (total score, each domain, and responders (3,5, 7 points)), ESSPRI (total score, each symptom, and responders (1,2,3 points)), Schirmer test, unstimulated salivary flow), by treatment group according to the disease severity at baseline and background therapy in RS, on the W000-W013 period.

The ESSDAI score by domain and ESSPRI score by symptom will also be described at each visit and by treatment group (value and change).

The SF-36 score by domain and MFI score by domain will also be described at each visit and by treatment group (value and change).

The STAR and CRESS scores will be described by domain at W013 and by treatment group

The clinESSDAI total score will be described at each visit and by treatment group (value and change).

IGG will be described at each visit and by treatment group (value and change).

For ESSDAI, the number and percentage of patients changing disease severity class between two timepoints (between W000 and W004, between W004 and W013 and between W000 and W013) will be described: No change / From mild to moderate / From mild to severe / From moderate to severe / From severe to moderate / From severe to mild / Form moderate to mild.

In the same way, for Schirmer test, the number and percentage of patients changing class between two timepoints (between W000 and W013) will be described: No change / From normal to grey zone / From normal to dry / From grey zone to dry / From dry to grey zone / From dry to normal / Form grey zone to normal.

The ESSPRI score will be described in a contingency table comparing classes modalities (score < 5 vs score ≥ 5) at baseline with the same classes' modalities at W013 thus allowing to determine number and percentage of patients moving from one modality to another between baseline and W013.

4.4. Safety analysis

All safety analyses will be performed by treatment group in the Safety Set, on the ASSE-W013 and ASSE-W028 periods.

4.4.1. Adverse events

Definition:

- **Treatment Emergent Adverse Events (TEAE)** on the ASSE-W013 period are defined as all adverse events:

- Which occur between the infusion start date/time of the first IMP intake (included) and the date of W013 visit (included) or the last IMP intake date + 21 days (included) if the W013 visit has not been done

or

- Which occur before the infusion start date/time of the first IMP intake and which worsen (in terms of intensity) or become serious according to the investigator opinion between the infusion start date/time of the first IMP intake (included) and the date of W013 visit (included) or the last IMP intake date + 21 days (included) if the W013 visit has not been done.

Of note, in case of multiple information of the same event before the first IMP intake date, the information nearest to the first IMP intake date is taken into account.

- **Treatment Emergent Adverse Events (TEAE)** on the ASSE-W028 period are defined as all adverse events:

- Which occur between the infusion start date/time of the first IMP intake (included) and the last IMP intake date + 85 days (included),

or

- Which occur before the infusion start date/time of the first IMP intake and which worsen (in terms of intensity) or become serious according to the investigator opinion between the infusion start date/time of the first IMP intake date (included) and the last IMP intake date + 85 days (included).

Of note, in case of multiple information of the same event before the first IMP intake date, the information nearest to the first IMP intake date is taken into account.

Analysis:

Number of events, number and percentage of patients reporting at least one event, presented by primary system organ class, and/or preferred term (depending on the analysis), will be provided for:

- Serious adverse events (SAE) over the analysed period according to the investigator or sponsor opinion.
- Adverse events of special interest.
- Treatment Emergent Adverse Event (TEAE).
- TEAE leading to IMP withdrawal.
- TEAE requiring new treatment or increase of on-going treatment.
- TEAE requiring surgical or medical procedure.
- TEAE related to IMP.
- TEAE related to Pss.
- Serious TEAE.
- Serious TEAE related to IMP.
- TEAE of Grade 3-4 intensity.
- Non serious TEAE over the corresponding treatment period.

TEAE will be described according to the seriousness, the intensity, the relationship with the IMP, the action taken regarding the IMP, the requirement of added therapy and the outcome. TEAE will also be described by time to onset according to the following classes: [0-4],]4,13] and > 13

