1. INTRODUCTION

This Statistical Analysis Plan deals with the main analysis of the study (ASSE-W013 period) and the follow-up period (ASSE-W028) and details the planned analyses to be performed, in accordance with the main characteristics of the amended study protocol version 4.0 dated from 24/03/2022.

The templates for Tables, Listings and Graphs (TLG) are described in a separate document.

The main analysis of the study concerns the ASSE-W013 period and will be performed as soon as all efficacy and safety data of the ASSE-W013 period are available and the mandatory steps required for study unblinding have been performed. The descriptive analysis including data after W013 will be performed subsequently when all data are available.

Of note, this SAP does not cover analyses of data associated to some exploratory objectives and the pharmacokinetics and pharmacodynamics data analyses described in the study protocol.

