3.2. General definitions

Patients having taken at least one dose of IMP correspond to patients with at least one date of first and/or last IMP intake complete or partially complete.

Analysable value will be defined as any non-missing value, except for:

- Laboratory parameters:
 - A laboratory value is considered as analysable if non-missing and not flagged in the ClinTrial database as "not analysable".
 - Vital signs value is considered as analysable if collected under appropriate circumstances (corresponds to the item of the source database).

Baseline value will be defined as the last analysable value prior to the first IMP intake. In case of patient included and/or randomised but not having taken at least one dosage of IMP: value at baseline is defined as the last analysable value prior or equal to date of inclusion visit.

Considered periods are:

- ASSE-W013 period.
- ASSE-W028 period.

Last post-baseline value under treatment of the period will be defined as the last post-baseline analysable value under treatment during the considered period.

Change from baseline to post-baseline visit is calculated as: Value at the post-baseline visit - Value at baseline.

Change from baseline to post-baseline visit under treatment is calculated as: Value at the post-baseline visit under treatment - Value at baseline.

Change from baseline to last post-baseline value under treatment is calculated as: Last post-baseline value under treatment - Value at baseline.

For safety endpoints (except adverse events), the following definition will be applied:

- **High emergent abnormal value under treatment according to the laboratory reference ranges** is defined as value \leq ULN (Upper Limit of Normal laboratory reference range) or missing at the baseline of the treatment period and $>$ ULN under treatment.
- **Low emergent abnormal value under treatment according to the laboratory reference ranges** is defined as value \geq LLN (Lower Limit of Normal laboratory reference range) or missing at baseline of the treatment period and $<$ LLN under treatment.

- **High emergent abnormal value under treatment according to the cut-offs for PCSA** values is defined as value \leq ULS (Upper Limit used to define potentially clinically Significant abnormal values) or missing at baseline of the treatment period and $>$ ULS under treatment.

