4.4.2. Clinical laboratory evaluation

4.4.2.1. Blood samplings for haematology, biochemistry and coagulation

For each laboratory parameter, the following analyses will be performed:

- Descriptive statistics on value at baseline, on value at each post-baseline visit under treatment, on last post-baseline value under treatment and on change from baseline to last post-baseline value under treatment. These analyses will be performed on both periods (ASSE-W013 and ASSE-W028) only for haematology parameters and on ASSE-W028 for other parameters.
- Number and percentage of patients with at least one high/low emergent abnormal value under treatment, according to the laboratory reference ranges and to the cut-offs for PCSA values.
- Laboratory parameters classified (number and percentage of patients in each class) according to these reference ranges and cut-offs and using shift tables from baseline to the worst (high and/or low) values under treatment.

Moreover, listings of patients with out-of-range or PCSA analysable values emergent under treatment and of non-analysable values excluded from analyses will be provided.

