7.1.1. Value prior to treatment / under treatment

Table (7.1.1) 1 - Definition of value prior to treatment

General definition	
For assessments without time collected Corresponding assessment date \leq date of the first IMP intake + X1 _{sup} days	X1 _{sup} = 0
For assessments with time collected Corresponding assessment date/time \leq infusion start date/time of the first IMP intake + X1 _{sup} days	
Specific definition	
For ESSDAI, ClinESSDAI and PhGA Corresponding assessment date = date of visit at W000 \leq date of the first IMP intake + X1 _{sup} days	
For ESSPRI, MFI, PGA, SF-36 Corresponding assessment date = date of visit at W000 \leq date of the first IMP intake + X1 _{sup} days	

Table (7.1.1) 2 - Definition of value under treatment

General definition	
For assessments without time collected	
On W000-W013 Period if W013 visit done Date of first IMP intake + X1 _{sup} ^(*) days \leq Corresponding assessment date \leq Date of W013 visit + X2 _{sup} days	X2 _{sup} = 0
On W000-W013 Period if W013 visit not done Date of first IMP intake + X1 _{sup} ^(*) days \leq Corresponding assessment date \leq Date of last IMP intake on the W000-W013 period + X2 _{sup} days	X2 _{sup} = 21
On W000-W028 Period Date of first IMP intake + X1 _{sup} ^(*) days \leq Corresponding assessment date \leq Date of last IMP intake on the W000-W028 period + X2 _{sup} days	X2 _{sup} = 85
For assessments with time collected	
On W000-W013 Period if W013 visit done Infusion start date/time of the first IMP intake + X1 _{sup} ^(*) days \leq Corresponding assessment date/time \leq Date of W013 visit + X2 _{sup} days	X2 _{sup} = 0
On W000-W013 Period if W013 visit not done Infusion start date/time of the first IMP intake + X1 _{sup} ^(*) days \leq Corresponding assessment date/time \leq Date of last IMP intake on the W000-W013 period + X2 _{sup} days	X2 _{sup} = 21
On W000-W028 Period Infusion start date/time of the first IMP intake + X1 _{sup} ^(*) days \leq Corresponding assessment date/time \leq Date of last IMP intake on the W000-W028 period + X2 _{sup} days	X2 _{sup} = 85

^(*) cf. definition of value prior to treatment.

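### On the SAP text, on-schedule W028 laboratory and vital-sign values, and non-serious, non-AEOSI events starting more than 85 days after the last infusion, enter no planned safety table

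*SAP*

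**What the plan says.** SAP 4.4 sets the scope: "All safety analyses will be performed by treatment group in the Safety Set, on the ASSE-W013 and ASSE-W028 periods". SAP 1 adds: "The descriptive analysis including data after W013 will be performed subsequently when all data are available". The safety endpoint in Protocol 3.4 and SAP 1.1.2 covers change over time and abnormal values across the whole study.

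For the ASSE-W028 period, SAP 4.4.1 counts an adverse event as treatment-emergent only up to "the last IMP intake date + 85 days (included"). SAP Table (7.1.1) 2 ends the under-treatment window at "Date of last IMP intake on the W000-W028 period" plus 85 days.

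The summaries then use that window:

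- **Blood tests (SAP 4.4.2.1):** descriptive statistics are given "on value at each post-baseline visit under treatment, on last post-baseline value under treatment". The emergent-abnormality table, the shift tables and the out-of-range/PCSA listing carry the same limit. Haematology is described on both periods, but descriptive statistics are "on ASSE-W028 for other parameters".
- **Urinary parameters (SAP 4.4.2.2) and vital signs (SAP 4.4.3.1):** same restriction.
- **By-visit laboratory rule (SAP 7.2.3.2):** W028 is among the visits to which samples are assigned, but only values measured under treatment are kept for the by-visit description.
- **Last value (SAP 3.2):** "the last post-baseline analysable value under treatment during the considered period".
- **Adverse events (SAP 4.4.1):** tables are limited to treatment-emergent events, except SAEs over the analysed period and AEOSI, which carry no such limit as worded.

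**The concern.** Laboratory tests and vital signs are collected at W028 (Protocol 8.2), and all adverse events up to the last study visit (Protocol 8.9.1). If W028 lies outside the window, tables labelled ASSE-W028 contain nothing from the last safety visit, and the W028 row foreseen in SAP 7.2.3.2 is empty. For biochemistry and coagulation, the ASSE-W028 tables are the only by-visit description planned.

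This is the first study in this disease, and lymphopenia and infection are named risks (Protocol 2). The protocol expects almost no pharmacological effect at W028, so that visit is well placed to show, by arm, whether counts have moved back towards baseline. Late grade 1-2 infections would be recorded but not tabulated.

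**Working it through.** **Inputs.** W000 = day 0. Last planned infusion W010 = day 70 ± 2; W013 = day 91; W019 = day 133 ± 7; W028 = day 196 ± 7, with windows counted from W000 (Protocol 4.1.2). After early discontinuation, follow-up visits come 9 and 18 weeks after the last infusion (Protocol 4.1.2, 5.6.1). The window is 85 days (SAP 4.4.1, Table (7.1.1) 2). Healthy-volunteer half-life is 111 to 280 h (Protocol 2).

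**The plan's own figures.** The companion 21-day limit, used when W013 is not done, reproduces: (13 − 10) × 7 = 21. The 85-day figure does not follow from any stated input: W028 − W010 = 126 days; 15 weeks = 105; 12 weeks = 84; five half-lives = 5 × 111/24 = 23.1 to 5 × 280/24 = 58.3 days.

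**End of window.** 70 + 85 = day 155; 155/7 = week 22.1.

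**Visits against the window (days after last infusion).**

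| Visit | Nominal | Range | Within 85? |
|---|---|---|---|
| W019 | 133 − 70 = 63 | 126 − 72 = 54 to 140 − 68 = 72 | Yes |
| W028 | 196 − 70 = 126 | 189 − 72 = 117 to 203 − 68 = 135 | No |
| 9 weeks, early discontinuation | 63 | 56 to 70* | Yes |
| 18 weeks, early discontinuation | 126 | 119 to 133* | No |

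*Assumes the ± 7 days given for W019 and W028 also applies here.

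**Size of the gap.** Nominal 126 − 85 = 41 days. For W028 the range is 117 − 85 = 32 to 135 − 85 = 50 days. For the 18-week visit it is 119 − 85 = 34 to 133 − 85 = 48 days.

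**Share of follow-up.** W013 to W028 is 196 − 91 = 105 days. The window covers 155 − 91 = 64 of them (64/105 = 61%) and leaves out 41 (39%).

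**Visits lost.** W028 is 1 of 2 follow-up visits. It is 1 of 7 post-baseline visits for blood tests, urinalysis, pulse, blood pressure and temperature (W002, W004, W007, W010, W013, W019, W028). For weight and BMI it is 1 of 5 (W004, W010, W013, W019, W028).

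**Consequences.** The last under-treatment value in the ASSE-W028 tables is in practice W019, unless a later unscheduled sample falls within 85 days. The last time-to-onset class for treatment-emergent events (> 13, presumably weeks) ends at about week 22.

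**The case against.** **The restriction comes from the protocol.** Protocol 10.1.2.5.2 and 10.1.2.5.3 already limit these summaries to under-treatment values, and 10.1.2.5.1 ties the adverse-event tables other than SAEs to emergent events. A reader might infer that the SAP contradicts the protocol, or itself. The documents do not support that. The protocol gives the restriction no end date and the SAP supplies one; SAP 3.2 treats under-treatment values as a subset of the period. What stands is that the consequence for W028 is not handled.

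**A reader might infer that 85 days is too short.** It exceeds five healthy-volunteer half-lives by 85 − 58.3 = 26.7 to 85 − 23.1 = 61.9 days. Those half-lives are not from patients, but nothing shows the window to be wrong. The missing explanation is a matter of detail, and a basis may exist outside these documents.

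**A reader might infer that nothing after the window is reported.** That is too broad. SAEs over the analysed period, AEOSI as worded, ADA and IL-7 at W028, and treatments started after the last infusion are all summarised. Grade 3 or higher lymphopenia and infections are AEOSI and remain covered. Clinically significant laboratory abnormalities are recorded as adverse events (Protocol 8.2), so serious ones reach the SAE table.

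**The TLG templates may supply the tables.** They are a separate document and were not available, so the point is limited to the SAP text. SAP 7.2.3.2 suggests that a W028 row was intended, but the rule as written empties it.

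**W028 values may reflect later therapy.** This is true, and it is a reason to label them rather than omit them.

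**Conclusion.** The point holds for the SAP text. Every on-schedule W028 visit lies 32 to 50 days beyond the window. The nominal 18-week visit after early discontinuation lies 41 days beyond it (34 to 48 if the ± 7-day tolerance applies). No laboratory, urinary or vital-sign table, and no out-of-range/PCSA listing, is planned for those values, which could concern up to 45 patients. Adverse events starting after day 85 that are neither serious nor of special interest have no planned table.

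The data are collected and only their reporting is missing. The conclusion rests on visits kept within their windows and on the absence of further tables in the TLG document. It says nothing against the length of the window. It affects descriptive safety reporting only, with no effect on efficacy results, and is best classed as a cheap improvement.

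**What to change.** Keep last infusion + 85 days for the treatment-emergent, emergent-abnormality and worst-value tables. For the ASSE-W028 period, add:

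1. By-visit values and change from baseline at W028, or at the second follow-up visit after early discontinuation, for laboratory, urinary and vital-sign parameters. Drop the under-treatment filter for these and label them post-treatment. SAP 3.2 already has the definition needed: "Change from baseline to post-baseline visit is calculated as: Value at the post-baseline visit - Value at baseline".
2. A listing of out-of-range/PCSA values that fall after the window.
3. A table by system organ class, preferred term and treatment group of adverse events with onset after last infusion + 85 days, up to the last study visit.

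If the TLG templates already contain these outputs, a sentence in the SAP saying so is enough.

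**Cost.** A few descriptive tables and one listing from data already collected; no existing definition or event count changes. The downside is that W028 values may reflect therapy started after the study drug: Protocol 6.3 bars the listed immunosuppressants and biologics only during study treatment, and Protocol 6.5 leaves later care to the physician. The new tables should therefore be read beside the summary of treatments after the last infusion that SAP 4.2.2 already plans.
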